Grade III and IV gliomas are considered aggressive primary brain tumors with a poor prognosis which depends on several factors. In particular, the most aggressive and malignant of the primary brain tumors are the so called Glioblastoma Multiforme (GBM), that are classified as WHO grade IV gliomas¹. GBMs accounts for 69% of all gliomas and for 12-15% of all primary brain tumors². Patients with GBM have a poor median overall survival (OS) of 14-16 months with gross total surgical resection and adjuvant chemo-radiation therapy. Nowadays, there are no curative treatments and tumor recurrence is expected. The use of alkylating agents has improved the prognosis of HGGs but after the introduction of Temozolomide (TMZ) in 2005 as standard first line treatment, no other improvement has been made³. Moreover, so far, there is not a standardized second line treatment after tumor recurrence and several drugs or treatment strategies are available⁴.

GBMs have been found to have a small population of cancer stem cells (CSC) that contribute to tumor spreading, invasion, proliferation and maintenance. In particular, CSCs seem to be responsible for cancer resistance to adjuvant treatments and such resistance is responsible for tumor recurrence during the neuro-oncological follow-up^{5,6}.

Features of drug resistance can also be transmitted cell to cell by the cross-linking network sustained by microvesicles (MV) like exosomes and large oncosomes (LO) that transport a varied population of proteins, lipids, DNA, and RNA species⁷ that enhance and influence mechanisms involved in drug resistance⁸⁻¹⁰. Among the molecules that can be transported by this MV network there is H⁺ Vacuolar ATPase (V-ATPase), a multisubunits proton pump that is mainly involved in the acidification of endosomes and lysosomes in eukaryotic cells. It is made of a membrane-embedded VO sector, which regulates protons permeability, and an enzymatic V1 ATPase sector¹¹⁻¹³.

In case of tumors, the role of V-ATPase seems to be crucial in order to maintain a normal intracellular pH in a metabolic setting based on anaerobic glycolytic reactions¹³. In fact, due to loss of functions of mitochondria during tumorigenesis, metabolism of neoplastic cells is based on anaerobic glycolysis which can easily afford ATP through the consumption of glucose but that, on the other hand, leads to production of lactates. The excess of lactates would determine a reduction of the intracellular pH and, consequently, activation of apoptotic reactions leading to the death of neoplastic cells¹⁴. In this setting, the excess of protons is counterbalanced by the extrusion of H⁺ from the intracellular to the extracellular environment through the activation and overexpression of V-ATPase. For this reason, many tumors show a V-ATPase overexpression, whose inhibition is related to a dysregulation of cytosolic pH that ultimately leads to the activation of pro-apoptotic proteins, alteration of metabolic chain reactions and of endosomal vesicles^{14,15}. Other than providing those functions, V-ATPase plays a crucial role in chemoresistance of solid tumors. In fact, excess of protons in the extracellular space determines a reduction of pH that can reduce the penetration and the efficacy of chemotherapeutic agents^{15,16,16}. Moreover, in few studies on breast cancer, B cell leukemia and melanoma, inhibition of V-ATPase have proved to increase the drug efficacy *in vitro*¹⁵. In addition, it is supposed that V-ATPase can act as a pump for extrusion of chemotherapy drugs from the intra-cellular to the extra-cellular compartment^{15,16}.

STUDY NAME: Vacuolar ATPase and drug resistance of high grade gliomas: a study to investigate possible therapeutic roles for proton pump inhibitors. STUDY CODE: GLIODRUG-V	Ver. 1.0 07/06/2019
---	------------------------

In 2015 Di Cristofori and colleagues demonstrated how V-ATPase is overexpressed in HGGs while it is poorly expressed in LGGs. From a clinical point of view, it was demonstrated how expression of V-ATPase is related to the patient's prognosis independently from other clinical risk factors. Moreover, it has been demonstrated that blocking the V-ATPase with specific drugs, in *in vitro* patient-derived GBM cultures, increased the efficacy of TMZ if compared with TMZ alone¹⁷.

Highly tumorigenic glioma stem cells secrete in their microenvironment many micro- and macrovesicles that are loaded with factors able to influence the behavior of cells in the tumoral niche and cells of the immune system. In particular, GBMs secrete LOs loaded with the homeobox genes POU3F2 and HOXA10 and with the V-ATPase subunit V1G1⁹. Interestingly, such LOs were found to be able to reprogram both neoplastic and non-neoplastic cells toward an oncogenic state through the activation of proliferative and motility pathways⁹. So far, it seems that configuration or expression of specific subunits might influence the tumor formation or the tumor aggressiveness, probably via Homeobox genes⁹. In fact, another study by Bertolini and Colleagues, reported that neurospheres with high levels of V-ATPase expressed high levels of homeobox genes (HOXA7, HOXA10, SHOX2, and POU3F2) In this setting, V-ATPase can be considered a key player involved in multiple functions that are necessary to afford CSCs survival and tumor progression. Virtually, V-ATPase is considered a possible target to sabotage the neoplastic metabolic machinery. In addition, inhibition of V-ATPase is considered a possible strategy to increase efficacy of antineoplastic drugs. This aspect of V-ATPase has not been studied in gliomas¹⁴.

With these premises, the aim of this study is to understand the possible role for proton pump inhibitors (PPI) as adjunctive treatments for high grade gliomas.

2. Experimental Design

2.1 Study Rationale

GBMs are still considered tumors with few available treatment options that are able only to achieve a temporary local control of the disease. In case of a GBM, tumor recurrence is generally expected within 12 months and it is due to the presence of marginal tumoral cells with pro-oncogenic molecular phenotypes that are resistant to actual chemotherapies and to radiation therapy^{5,18,19}. In particular, according to the study of Persano and Colleagues, in case of GBM it is possible to distinguish three neoplastic layers within the tumor that show different molecular patterns: the central core; the intermediate layer and the peripheral layer⁵. Nowadays, surgery still represent the first treatment option in case of suspected GBM and it aims to remove the contrast enhancing lesion seen at the pre-operative brain MRI. In particular, the peripheral layer is made of low replicating cells and it can be considered normal when tissue sampling is made far from the tumor cavity⁵. In fact, Clavreul et al. in 2015 demonstrated that peripheral GBM layer contains glioblastoma-associated stromal cell (GASC) that can show different carcinogenic properties and that are probably responsible for tumor recurrence²⁰⁻²². These findings can be considered in line with previous studies that showed some invasive tumor cells, various types of reactive cells, and angiogenesis with different immunophenotypes in peritumoral brain edema²³.

Nevertheless, some research teams are trying to understand if surgical removal of peritumoral FLAIR hyperintensity is able to reduce the tumor recurrence rate prolonging the OS²⁴.

STUDY NAME: Vacuolar ATPase and drug resistance of high grade gliomas: a study to investigate possible therapeutic roles for proton pump inhibitors. STUDY CODE: GLIODRUG-V	Ver. 1.0 07/06/2019
---	------------------------

Metabolism of GBMs is mainly anaerobic and it is sustained by glycolysis²⁵. Anaerobic glycolysis is a simple metabolic reaction that leads to the transformation of glucose in ATP and lactates. Glucose is delivered to the tumor through neoangiogenetic processes²⁶. Production of a significant amount of lactates determines a decrease of intracellular pH that is counterbalanced by V-ATPase activity through the extrusion of H⁺ ions from the intracellular to the extracellular environment. In vitro inhibition of V-ATPase has proved to increase CSC apoptosis due to decrease of intracellular pH¹⁷.

Moreover, increased V-ATPase activity determines an extrusion of H⁺ ions in the extracellular environment that can positively affect different pro-tumoral activities. In fact, a decrease of extracellular pH leads to activation of proteases able to destroy the extracellular matrix. Such activity enhances tumor spreading. Moreover, a low extracellular pH can reduce the efficacy of antineoplastic agents since a low pH might affect the structural integrity of drugs and their ability to pass through the plasmatic membrane. Finally, V-ATPase can act as an active pump able to excrete antineoplastic agents¹⁵.

For this reason, PPIs are considered new anti-cancer drugs able to increase tumoral cell death, reduce tumor invasion and increase chemotherapy efficacy¹⁴.

Moreover, GBMs with high V-ATPase expression has proved to be able to transmit highly malignant features through a network of MVs and to activate proliferation of GASC *in vitro* through the transmission of G1 subunit of V-ATPase^{9,27}.

In this view, our work is intended to study: 1) the effects of PPIs on CSC and GASCs cultures as in vitro add-on treatments; 2) the MVs load in terms of miRNAs and DNA (ssDNA, exoDNA²⁸) during the neuro-oncological follow-up in order to understand how it changes after surgery and adjuvant treatments; 3) the possible roles of V-ATPase as a clinical marker to be used to check tumor response to adjuvant treatments.

2.2 Objectives

- **Primary objective:** to determine and investigate the role of V-ATPase in drug resistance and the role of proton pump inhibitors as add-on treatment for high grade gliomas “*in vitro*” on CSC cultures obtained both from tumor and peritumoral margins.
- **Secondary objective:** to determine whether MVs content in human blood is similar to the MVs content in CSCs “*in vitro*” in order to study the mechanisms of tumor recurrence and in to study possible translational aspects of our research.
- **Tertiary objective:** to determine whether mechanisms of drug resistance can be transmitted via the cross-linking network sustained by exosomes and how this network is regulated in relation to the expression of V-ATPase.

2.3 Type of Study

This is a prospective observational cohort study on biological materials.

2.4 Study Population

Planned number of subjects undergoing surgical removal of intra-axial brain tumor at the Neurosurgical Division of Ospedale San Gerardo: almost 45 per year. Thirty patients are expected to have a glioma of which 25 patients are expected to be diagnosed with a GBM and 5 with a LGG. We plan to enroll 25 patients/year.

STUDY NAME: Vacuolar ATPase and drug resistance of high grade gliomas: a study to investigate possible therapeutic roles for proton pump inhibitors. STUDY CODE: GLIODRUG-V	Ver. 1.0 07/06/2019
---	------------------------

2.5 Inclusion Criteria

- Patients => 18 years old;
- Patients with an intra-axial brain tumor suspect for glioma;
- Patients able to sign a consent form for research purpose;
- Patients with planned craniotomy for brain tumor resection.

2.6 Exclusion Criteria

- Patients < 18 years old;
- Patients with known brain tumors different than gliomas;
- Patients unable to sign a consent form for research purpose;
- Patients undergoing brain tumor biopsy;
- Patients with poor intra-operative or small surgical sample for histopathological diagnosis;
- Histology diagnostic for tumors different than gliomas.

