2.7 Experimental Design

Our study will use glioma tissues, after all sampling for diagnosis will be collected. Moreover, we will take blood samples from patients undergoing surgery for HGGs and during the oncological follow-up. Tumor samples will be harvested in order to obtain parallel tumor cultures to test *in vitro* tumor sensitivity to different chemotherapies, with and without inhibition of V-ATPase. Moreover, we will analyze the expression of V-ATPase (especially subunit V1G1) in vesicles released by cancer cells, in order to understand how V-ATPase can influence drug resistance and tumor progression. HGG-released vesicles will be also isolated in the circulation from patients' blood in order to analyze tumor responses to oncological treatments and the genetic and epigenetic status of the tumor, including amplification of oncogenes (i.e. *c-Myc*), and the content of specific coding and non-coding RNA, DNA and retrotransposon elements, through the use of next generation sequencing (NGS)²⁸.

Duration for enrollment: 24months;

Duration for follow-up analysis: 12 months for each patient.

Maximum length of the study: 36 months including patients' follow-up

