3.4 Surgical methodology

Patients will be operated for intra-axial brain tumors. Part of the tumor specimen, will be sent for cell culture; while the majority of the tumor specimen will be used for a formal histological diagnosis. In order to achieve a gross total resection and confirm it histologically, a sample of marginal tissue of the surgical bed will be sent for cell culture and histology. Marginal tissue will be collected from non eloquent brain areas. Intraoperative ultrasound will be used to check presence or absence of high cellularity of the sample.

Patients with brain tumors other than gliomas at histological diagnosis will be excluded from the study. Sample of these tumors will be eliminated.

If the tissue removed from the patient enrolled in this study will not allow to perform the sample for the study without affecting the optimal histological diagnosis, the patient will be excluded from the study and no sampling will be executed.

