3.5 Tissue and blood samples preservation, storage and management

3.5.1. Sampling and analysis

Part 1 – stem cell cultures sampling and processing

Biological samples from patients undergoing surgery for intra-axial brain tumor will be taken and processed. Tumor margins will be collected as well, in order to check tumor resection with histopathological findings and in order to investigate the role of CSCs in the brain adjacent to tumor in determining the tumor recurrence due to resistance to treatments. Both tumor area and its marginal tissue will be taken during the surgery and collected for laboratory procedures and histological analysis. Blood samples will be collected 1-3 days before surgery and 1-3 days after surgery and will be processed for serum collection and stored for further analysis on MVs.

The fresh tissue (tumor and marginal tissues) will be treated in order to obtain single cell suspensions and neurospheres. Then, each patient-derived primary cell cultures will be expanded and subsequently divided into 2 parts: 1) one destined to CSCs cultures for *in vitro* tests; 2) one for biological storage, for further retrospective analyses. The storage of biological samples will be at the Medical Genetics Laboratory ([name]), of School of Medicine and Surgery, University of Milano-Bicocca. All the materials for

STUDY NAME: Vacuolar ATPase and drug resistance of high grade gliomas: a study to investigate possible therapeutic roles for proton pump inhibitors. STUDY CODE: GLIODRUG-V	Ver. 1.0 07/06/2019
---	------------------------

the study will be provided by the same laboratory, so there are no additional costs for the Neurosurgical Division and for Hospital San Gerardo.

Part 2 - in vitro study of drug resistance

Neurospheres from marginal tissues will be obtained by co-culturing of marginal tissue with MVs taken from CSCs cultures medium, in order to better define the role of V-ATPase in drug resistance and the role of MVs in transferring drug resistant phenotypes from a CSCs culture to another.

CSCs cultures will be treated with antineoplastic drugs with and without PPI. In this way, it will be possible to understand the *in vitro* response to antineoplastic agents and PPI.

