STUDY NAME: Vacuolar ATPase and drug resistance of high grade gliomas: a study to investigate possible therapeutic roles for proton pump inhibitors. STUDY CODE: GLIODRUG-V	Ver. 1.0 07/06/2019
---	------------------------

MVs isolation will be performed as reported below.

For all patients 20 mL fasting blood sample will be collected in a sterile vacuum tube. The collection will be done in the same time of routine preoperative blood samples or planned follow-up controls, since no others invasive procedure should be required from the patients since their enrollment in the study. The blood sample will be stored at 4°C and handled within 6 hours. Then, 5 mL will be centrifuged at 3000 rpm for 10 minutes at 4°C, the plasma phase will be collected and aliquoted in 1.5 mL sterile tubes and stored at -80°C until use or shipment. Then, we will isolate peripheral blood mononucleate cells (PBMC) through Ficoll gradient from the remaining 15 mL. After isolation, live PBMC will be frozen in standard media 20% Fetal Bovin Serum (FBS) 10% Dymethyl Sulfoxide (DMSO) and stored in liquid nitrogen until use. All these parts of the experiment will be performed at the Medical Genetics Laboratory ([name]), of School of Medicine and Surgery, University of Milano-Bicocca.

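### The question concerns high grade glioma, but the criteria keep low grade glioma; if those patients enter the exploratory marker-outcome analyses, log-rank and ROC results could partly reflect grade

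*Protocol*

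**What the plan says.** **Target.** The title and 2.2 are about HGG; the primary objective includes "the role of proton pump inhibitors as add-on treatment for high grade gliomas".

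**Eligibility.** Section 2.5 admits adults with a suspected glioma, with no limit on grade. The tumour-type exclusions in 2.6 are "Patients with known brain tumors different than gliomas" and "Histology diagnostic for tumors different than gliomas". Section 3.4 repeats the rule: "Patients with brain tumors other than gliomas at histological diagnosis will be excluded from the study". Section 2.8 withdraws a patient who later meets an exclusion criterion, and LGG is not one.

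**Numbers.** Of 30 gliomas expected each year, 2.4 says "25 patients are expected to be diagnosed with a GBM and 5 with a LGG". It then plans 25 enrolments a year without naming the grades. Section 2.7 gives 24 months of enrolment and 12 months of follow-up per patient.

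**Blood.** Section 2.7 says "we will take blood samples from patients undergoing surgery for HGGs" and goes on to speak of vesicles released by HGG. Section 3.5.1 says "For all patients 20 mL fasting blood sample will be collected in a sterile vacuum tube", and also "Blood samples will be collected 1-3 days before surgery and 1-3 days after surgery".

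**Follow-up.** Section 3.7 describes a single first-line course for every patient, although 3.1.2 records previous surgery.

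**Analysis.** Section 3.8 plans Kaplan-Meier curves, log-rank comparisons, ROC analysis with a Youden cut-off, logistic or Cox models, and an optional propensity-score step. Grade is not mentioned there. It is collected under 3.1.7.

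**The concern.** The study population and the study question do not match, and the text does not say which governs the clinical analyses. That matters where a marker is related to outcome, a use that appears in 2.1 (V-ATPase as a clinical marker of response) and in 3.5.1 Part 3 (new markers for recurrence).

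The Introduction supplies both links needed for confounding, at least for V-ATPase expression: it is high in HGG and low in LGG, and grade III-IV tumours have a poor prognosis. If LGG are analysed together with HGG, low-expressing patients with longer survival gather in the low-marker group. An unadjusted log-rank test can then be significant with no marker effect inside either grade, and a Youden cut-off can partly separate grades instead of outcomes within HGG.

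The conflicting blood-sampling text leaves open whether LGG would be in the vesicle analyses at all.

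**Working it through.** **1. The forecast in 2.4**
- 25 GBM + 5 LGG = 30 gliomas a year, as stated. Grade III: 30 - 25 - 5 = 0, although the Introduction groups grades III and IV together.
- Enrolment over 24 months: 25 x 2 = 50. Gliomas forecast: 30 x 2 = 60.
- LGG among the 50: minimum 0 (25 a year equals the GBM forecast); maximum 5 x 2 = 10; in proportion, 50 x 5/30 = 8.3.
- HGG among the 50 is therefore 40 to 50, or about 42 in proportion.

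**2. The blood passages side by side**
- Section 2.7 names HGG surgery; the handling paragraph of 3.5.1 names all patients.
- The first draw comes 1-3 days before surgery, before histology. An HGG limit therefore cannot govern that draw. It can govern only whose sample is analysed or followed, and the text does not say that it does.

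**3. Illustration of the possible size.** The Protocol states no power, effect size or event count to reproduce, so this is a simulation with declared assumptions.
- From the Protocol: N = 50; censoring at 12 months; HGG median overall survival (OS) 15 months, the middle of the 14-16 given for GBM; two-sided 5%.
- Assumed: HGG median progression 8 months; LGG median OS 60, 84 or 120 months; LGG median progression 36, 48 or 60 months; exponential times; a normal marker, lower in LGG by 0 to 2 SD, split at its median; no marker effect within grade.
- 12-month event risk = 1 - 0.5^(12/median). OS: HGG 0.43, LGG 0.07-0.13. Progression: HGG 0.65, LGG 0.13-0.21.
- Test: Z = (O - E)/sqrt(V), rejected when |Z| > 1.96. The stratified version sums O, E and V within grade. There were 10,000 runs per scenario.

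Log-rank false-positive rates:

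| LGG of 50 | Marker lower in LGG by | OS | Progression |
|---|---|---|---|
| 0 | not applicable | about 5% | about 5% |
| 4 | 1-2 SD | 5-6% | 6-8% |
| 8 | 0 | about 5% | about 5% |
| 8 | 0.5 SD | 6-7% | 6-7% |
| 8 | 1-2 SD | 7-12% | 9-18% |
| 10 | 1-2 SD | 8-15% | 11-26% |
| any, grade-stratified or HGG-only | any | 5-6% | 5-6% |

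With 8 LGG and a 1-2 SD difference, the mean area under the ROC curve for 12-month status rises from 0.50 to 0.54-0.59 (OS) and 0.57-0.62 (progression).

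**4. Sensitivity.** A separate run (3,000 per scenario, 8 LGG of 50, 1-2 SD) set the LGG 12-month event risk directly at 5-10% for both outcomes. It gave 7-12% for OS and 11-22% for progression, and 4.4-6.4% when stratified by grade. The progression figures are higher because that run assumes fewer LGG progressions than the 13-21% above.

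**The case against.** **Pooling is not stated.** A reader might infer that 3.8 pools the grades. It does not say so, and it names no marker or grouping for the log-rank test. It plans multivariable models that could include grade, and an optional propensity-score step. Covariates and analysis sets are often left to a statistical analysis plan, which may exist. This stands as a limit on the claim. It does not remove the point: who is eligible, who is withdrawn and whose blood is used are protocol matters on which the sections conflict, and a multivariable model does not adjust a log-rank test or a Youden cut-off.

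**The text leans towards HGG.** The title, 2.2 and 2.7 all name HGG, and 25 a year equals the GBM forecast. The vesicle sentence in 2.7 suggests that only HGG blood would be analysed, and the all-patients wording in 3.5.1 may mean only the patients sampled. On that reading no LGG enter the blood-marker analyses and the error rate stays near 5%. The reading is plausible, but no criterion enforces it.

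**The grade difference is in expression.** A reader might infer that the circulating vesicle markers are confounded too. The Introduction reports a difference by grade for V-ATPase expression. Whether vesicle content in blood differs by grade cannot be known from the document. This objection stands in full.

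**The sizes are assumed.** LGG outcomes, marker shift, LGG count and median split are not in the Protocol. The figures show what could happen and do not predict it.

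**Conclusion.** The mismatch holds on the text: an HGG question, criteria that keep any confirmed glioma, an enrolment figure that does not say which patients it counts, and two accounts of whose blood is taken. The statistical consequence is conditional. It needs LGG in the marker-outcome set and a marker that differs by grade. Given both, with 8 LGG and a 1-2 SD difference, the unadjusted log-rank error is about 7-12% for OS and 9-18% for progression under the stated assumptions. It is small with 4 or fewer LGG and about 5% if either condition fails.

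A reader might infer that the main result is at risk. The documents do not support that. The primary in vitro comparison, drug with and without V-ATPase inhibition, is made within each culture and is not confounded by grade. Predicting outcome from a marker is exploratory and is not among the objectives in 2.2. The point is minor to moderate.

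**What to change.** - In 3.8, define the set for marker-outcome analyses as histologically confirmed WHO grade III-IV glioma, with LGG reported separately. Alternatively, stratify the log-rank test and stratify or adjust the Cox model by the grade collected under 3.1.7, and give ROC/Youden results within HGG.
- Reconcile 2.4 to 2.7, 3.5.1 and 3.7 on who is enrolled, whose blood is analysed (as distinct from drawn before histology), and whom the follow-up description covers, including previously operated patients. No clinical rule is proposed here.
- Restate in 2.4 the expected number of HGG patients, including grade III.

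Enrolment on suspected glioma can stay.

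**Cost.** Wording only; no new data or samples. Restriction leaves about 42 instead of 50 patients in the main marker set if LGG enrol in proportion. Stratifying or adjusting by grade removes no patient from the log-rank or Cox analyses.
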